2.3 Exploratory Outcomes

1. Composite mean hierarchical-rank clinical score between dapagliflozin vs. placebo. All patients will receive a global rank endpoint based on time to death (tier 1) time to HF hospitalization or urgent HF visit (tier 2) or change KCCQ clinical summary score from baseline to 12 weeks
2. Number of heart failure hospitalizations
3. Number of urgent heart failure visits
4. Number of heart failure hospitalizations and urgent heart failure visits
5. Proportion of patients that progress to diabetes during the treatment period (within the subgroup of patients without diabetes at baseline only)
6. Change from baseline in average weekly loop diuretic dose (furosemide equivalent)
7. Change in NYHA Class at 6 and 12 weeks.
- 8.
9. Change from baseline in left atrial volume index and other measures of left ventricular diastolic function

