system, skin, musculoskeletal system, height (screening only), weight, pulse, blood pressure, monitoring for volume depletion, and assessment for ketoacidosis (difficulty breathing, nausea, vomiting, abdominal pain, confusion, and unusual fatigue or sleepiness).

- b) Screening laboratory assessment includes HbA1c, BNP, NTproBNP and renal panel.
- c) Randomization, Week 6 and Week 12 laboratory assessment includes HbA1c, Fasting Glucose, BNP, NTproBNP, CBC, renal panel, and collection of samples for future potential biomarker analyses (Randomization and Week 12 only).
- d) Week 13 laboratory assessment includes only renal panel.
- e) Only for women with childbearing potential.
- f) Phone visits include recording any AE or SAE, self-monitoring of weight and blood glucose (patients with established type 2 diabetes only), and encouraging compliance with study medication.
- g) Visit Windows: There may be up to 2 weeks between the screening and randomization visits. Week 6, 12 and 13 clinic visits have a +/- 2-day visit window. Phone Visits have a +/- 2-day visit window.
- h) An echocardiogram will be completed in those subjects participating in echo sub study at Visit 1 (Week 0 Randomization) and Visit 7 (Week 12)
- i) The urine specimens collected at 0, 6 and 12 weeks will only be checking urine albumin and urine creatinine. It will not be a standard urinalysis, and any clinical suspicion of urinary tract infection will be left to the local investigator or patient's primary care physician to order a proper screening test to evaluate.
- j) If a patient is a screen failure at the initial screening visit, they may be rescreened on three additional occasions at the discretion of the investigator. At the rescreening visit, the patient should be treated like a new patient and assigned a new subject number and all screening visit procedures should be completed, including obtaining informed consent.
- k) Subjects should be resting in the supine position for at least 5 minutes prior to collection of blood samples for biomarkers at Visit 1 (Week 0 Randomization) and Visit 7 (Week 12).
- l) For all patients, their most recent clinically available echocardiogram prior to study enrollment will be submitted using the WebPAX system, if feasible. This will be a historical Echo which is a part of the patient record and is independent to any study-related Echo image acquisition.

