4 STUDY POPULATION

Voluntary participation will be sought from patients with chronic heart failure with preserved systolic function at outpatient general cardiology and specialized heart failure clinics. Informed consent will be obtained from potentially eligible participants prior to initiating screening visit procedures.

It is expected that approximately 60% (174 patients) of the study cohort will have pre-diabetes or normal glucose metabolism (no diabetes), and therefore, the proportion of patients with established Type 2 diabetes may be capped at 45% (~146 patients). The proportion of patients with permanent atrial fibrillation may be capped at 33% of the study cohort (105 patients).

Randomization will be stratified by diabetes status (diabetes vs. no diabetes), permanent atrial fibrillation status (Yes vs. No), and by patients' participation in the echocardiography sub-study.

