2 GENERAL CONSIDERATIONS FOR DATA ANALYSES

2.1 Analysis Data Sets

Efficacy and safety analyses will be performed on data from the following analysis sets:

- Enrolled patients set (EPS) will consist of all patients who signed the informed consent. This data set will be used to summarize the patient disposition data.
- Modified intention to treat set (modified ITTS) is defined as all patients who have been randomized to study treatment, have received at least one dose of study medication, and have sufficient evaluable data for endpoint ascertainment during follow up. For clarity, patients with no evaluable data for a particular outcome during follow up will be excluded from the analyses of these respective endpoints. Subjects will be analysed according to the randomization group. The modified ITTS data set will be used for the primary, secondary, and selected exploratory (, NYHA class, loop diuretic dose, progress to DM, left atrial volume index and other measures of left ventricular diastolic function) efficacy endpoints. Progress to DM will be assessed among participants in the modified ITTS who had no diabetes at baseline. Left atrial volume index and other measures of left ventricular diastolic function will be assessed among participants who are in the modified ITTS dataset and also in the Echocardiography sub study.
- On-treatment set (OTS) includes all subjects in the modified ITTS. Primary and secondary endpoint measurements will be excluded for the follow-up time point(s) when subjects were temporarily or permanently off the study drug at the time the corresponding measurements were obtained. The OTS data set will be used for a sensitivity analyses for the primary, secondary, and selected exploratory (composite hierarchical rank clinical score, NYHA class, loop diuretic dose) efficacy endpoints.
- The per protocol set (PPS) includes all subjects in the modified ITTS who did not have any major protocol deviations. Major protocol deviations, which are detailed in section 2.2, will be determined prior to unblinding of treatment groups. Subjects will be summarized according to actual treatment received regardless of the allocated treatment. This will be used for a sensitivity analysis for the primary efficacy endpoints only.

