2.6 Missing Data

There are three possible sources for missing data:

1. Deaths
2. Administrative error
3. Premature study terminations

Missing data due to deaths is expected to be very low (fewer than 10 patients) because of the short follow-up period. Missing data due to administrative error is believed to be negligible due to the study management procedures and is also believed to be missing completely at random (MCAR). For patients who drop out of the study prematurely, a premature treatment discontinuation visit (PTDV) will be scheduled for them, whenever possible, to get the last assessment. The PTDV assessment will be carried forward to the next follow-up time point. For partially completed KCCQ questionnaires, the scoring algorithm accommodates a limited number of skipped responses. Values that are missing at randomization but available at screening will be imputed using the value at screening. Primary, secondary, and exploratory endpoints will be analyzed among patients for whom all relevant data for the given endpoint can be calculated.

For KCCQ scores, additional sensitivity analysis will be conducted using multiple imputation to account for missing values. IVEware (Raghunathan et al. 2002) will be used to perform the multiple imputation which employs iterative sequential regression to sample missing values from the predictive distribution of each variable, conditional on all other variables included in the imputation model. The following variables will be included in the imputation model: baseline KCCQ scores, sex, baseline eGFR, history of diabetes (DM), history of permanent AFib, baseline LVEF, baseline NYHA class, heart failure hospitalization during the trial duration, urgent heart failure visit during the trial duration, and covariates used as subgroup variables in section 2.3. Additionally, the imputation model will also include all follow up

assessments available for KCCQ scores, eGFR, NTproBNP, BNP, Hgb, loop Diuretic dose, 6-minute walk test.

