- Proportion of patients that progress to diabetes during the treatment period (within the subgroup of patients without diabetes at baseline only). Progression to diabetes is defined as a HbA1c of 6.5 or greater at either 6 week or 12 week follow-up.
- Average daily loop diuretic dose (furosemide equivalent)

The following equations will be used to convert doses to Furosemide equivalent:

- 40 mg Furosemide = 20 mg Torsemide = 2 mg Bumetanide = 50 mg Ethacrynic Acid
- When patient is not on a loop diuretic, dose = 0 mg.

- For subjects with dosing schedule reported as “as needed (prn)”, we will assume a twice a week dosing regimen for loop diuretic at the recorded dose.

In addition to comparing daily loop diuretic dose between treatment arms, we will also compare the proportion of patients who had their loop diuretic dose reduced or discontinued at any time during the treatment period.

- Change in NYHA Class at 6 and 12 weeks.

A 3-level categorical variable: 1) Decrease, 2) No change, 3) Increase. For patients missing NYHA class at 12 weeks, value at 6 weeks will be used.

- Echocardiography sub study endpoints: left atrial volume index and other measures of left ventricular diastolic function

Primary Endpoint

Left atrial volume index at 12 weeks

Exploratory endpoints:

- BSA
- LVEDD
- LVESD
- IVSd
- PWd
- Relative Wall Thickness
- LV Mass
- LV Mass Index
- Left ventricular end diastolic volume
- Left ventricular end systolic volume
- Estimated LVEF
- LVEF Calculated
- Left atrial dimension
- Left atrial volume
- Left atrial volume index
- E
- E/A
- E/E' medial
- E/E' lateral
- Tricuspid regurgitant velocity
- Longitudinal strain

5 Analyses of Baseline Characteristics

Patient demographics, baseline clinical characteristics, medical histories, and baseline labs will be described overall and by treatment group. Continuous measures will be summarized by mean \pm standard deviation and compared using Student's T-tests. Categorical variables will be summarized by frequency and percent and compared using χ^2 or Fisher's exact tests, as appropriate.

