3.3	Admission for an acute coronary syndrome (ST-elevation MI, non-ST-elevation MI, or unstable angina), percutaneous coronary intervention, or cardiac surgery during the study period.	Other	To be decided on a case by case basis
4. Patient received prohibited concomitant medication but study treatment not discontinued:			
4.4.1	SGLT2 inhibitors	Other	Only the efficacy endpoints before the start of prohibited medication will be included in PPS analysis
5. Patient received incorrect investigational treatment/dose			
5.0	Patient took incorrect treatment or damaged Investigational Drug Kit	MIA	To be decided on a case by case basis
5.1	Major compliance issues <80% or >120% compliance with IP dosing in double blind treatment period	MIA	To be decided on a case by case basis
5.2	Patient randomized but never took IP	MIA	To be decided on a case by case basis

5.3	Overdose	MIA	To be decided on the case by case basis
6. Protocol-required procedure not adhered to:			
6.0	Study data collection has not been stopped when subject decided to withdraw their consent from the study completely	Other	No exclusion from PPS Data collected after consent withdrawal to be excluded from data base
6.1	Patients with absence of NT-proBNP data at randomization visit and having values at Screening visit.	Other	No exclusion from PPS Values from screening visit will be used to impute the values at randomization visit.
6.2	Patients with absence of baseline NT-proBNP data at both screening and randomization visits	Other	Excluded from the NT-proBNP analyses
6.3	Patients with no NT-proBNP values after randomization	Other	Excluded from the NT-proBNP analyses
6.4	Patients with absence of baseline KCCQ clinical summary score at randomization visit	Other	Excluded from the ITTS KCCQ analyses
6.5	Patients with no KCCQ clinical summary score after randomization	Other	Excluded from ITTS KCCQ analyses
6.6	Patients with absence of baseline 6-minute walk assessment at randomization visit	Other	Excluded from the 6-minute walk analyses
6.7	Patients with no 6-minute walk assessment after randomization	Other	Excluded from 6-minute walk analyses
6.8	Patients with missing values in the covariates: gender, Hx AFib, AFib type, Hx DM, eGFR at randomization, lvef at randomization	Other	No exclusion from PPS Excluded from the first and second primary analysis

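### Progression to diabetes is scored from follow-up HbA1c alone, with no stated requirement that HbA1c was below 6.5 before treatment

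*SAP*

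**What the plan says.** The protocol names the endpoint without a threshold (Protocol 2.3): "Proportion of patients that progress to diabetes during the treatment period (within the subgroup of patients without diabetes at baseline only". The SAP supplies the event rule in 4.3: "Progression to diabetes is defined as a HbA1c of 6.5 or greater at either 6 week or 12 week follow-up". SAP 2.1 supplies the at-risk set: "Progress to DM will be assessed among participants in the modified ITTS who had no diabetes at baseline".

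No passage states how baseline diabetes status is determined. The nearest is Protocol 4, where roughly 60% of the "study cohort will have pre-diabetes or normal glucose metabolism (no diabetes" group is expected, with no laboratory cut-off. Elsewhere the SAP labels the variable as a history item: "history of diabetes (DM" in the imputation model (SAP 2.6) and "Hx AFib, AFib type, Hx DM, eGFR at randomization" in the missing-covariate rule (SAP 10.2, item 6.8).

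Pre-treatment HbA1c is available. Protocol 3.2, Table 1, footnote b puts it in the screening panel, and footnote c adds: "Randomization, Week 6 and Week 12 laboratory assessment includes HbA1c".

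SAP 6.3.5 analyses the endpoint as in 6.3.2: chi-square or Fisher's exact test, plus a Cox model adjusted for sex, eGFR, diabetes, permanent atrial fibrillation and LVEF. Baseline HbA1c is not among the covariates.

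**The concern.** Progression means moving from below the threshold to at or above it. The rule tests only the end state. A patient in the no-diabetes group whose HbA1c was already 6.5 or more before the first dose meets the definition by staying where they were.

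What is at stake is the meaning of the endpoint. Protocol 1.3.4 expects dapagliflozin to help glucose control in type 2 diabetes or prediabetes. If some already-elevated patients fall below 6.5 on drug while their counterparts on placebo do not, the arms differ, and the difference would be reported as diabetes prevented when no one had newly progressed. With few events expected, a handful of such patients could dominate the comparison. Both arms are affected alike under the null, so the false-positive rate is not inflated.

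**Working it through.** The plan gives no event rate, power or HbA1c distribution for this endpoint, so there is no stated figure to reproduce. The one document input is the size of the no-diabetes stratum: about 174 evaluable patients, 87 per arm (Protocol 12.2). Everything else below is assumed.

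**Step 1: does anything in the text close the gap?**
- Event rule (SAP 4.3): only week-6 and week-12 HbA1c enter.
- At-risk set (SAP 2.1, 4.3): no diabetes at baseline, with no HbA1c limit.
- Eligibility (Protocol 4.1, 4.2): no criterion uses HbA1c.
- Analysis (SAP 6.3.5 via 6.3.2): no baseline HbA1c term. The KCCQ responder model in SAP 6.2.6 does adjust for the baseline measurement.
- Timing: the randomization sample is drawn at the visit where the patient is randomized (Protocol 6.2.2) and is shipped to a central laboratory (Protocol 7.2), so the stratum can hardly depend on it.

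Nothing closes it.

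**Step 2: how many could be affected?** Assume true HbA1c is normal with mean m (5.7 to 5.9) and SD s (0.3 to 0.4), each measurement adds independent within-person error with SD w (0.1 to 0.2), and nobody truly changes. Under history-only classification, the expected number at 6.5 or more at randomization is 174 × [1 − Φ((6.5 − m)/√(s² + w²))]. For m = 5.8, s = 0.4, w = 0.15: √(0.16 + 0.0225) = 0.427, 0.7/0.427 = 1.64, upper tail 0.051, and 174 × 0.051 ≈ 8.8.

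Simulating screening, randomization, week 6 and week 12 under this model gives:

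| m / s / w | 5.7 / 0.3 / 0.1 | 5.8 / 0.4 / 0.15 | 5.9 / 0.4 / 0.2 |
|---|---|---|---|
| At 6.5 or more at randomization, of 174 | 1.0 | 8.8 | 15.7 |
| Share of these called progressors | 66% | 74% | 71% |
| Miscounted in this way | 0.7 | 6.6 | 11.1 |
| All calls | 1.5 | 12.4 | 22.7 |
| Miscounted, if screening HbA1c below 6.5 is already required | 0.2 | 2.0 | 4.0 |

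**Step 3: allow true new onset.** In the central case 6.6/12.4 = 53% of calls were already at 6.5 or more at randomization. That share has no real progressors in its denominator. Adding assumed new onset of 2% among the other 165 patients (3.3 events) gives 6.6/15.7 = 42%. Adding 5% (8.3 events) gives 6.6/20.7 = 32%. In the low case, 45% falls to about 13% and 7%.

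**Step 4: a second parameterisation.** Let p be the share already at 6.5 or more, q the probability of still being there at week 6 or 12, and r the new-onset rate. Counted events = 174·p·q + 174·(1 − p)·r. With q from 0.7 to 0.9 and r from 2% to 5%:
- p = 0: no event is affected.
- p = 2%: 2.4 to 3.1 events are not new, 22% to 48% of those counted.
- p = 5%: 6.1 to 7.8 events, 42% to 70%.
- p = 10%: 12.2 to 15.7 events, 61% to 83%.

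**Step 5: can it create an arm difference?** With p = 5%, no new onset, and assumed persistence of 90% on placebo and 60% on dapagliflozin: 87 × 0.05 × 0.9 = 3.9 against 87 × 0.05 × 0.6 = 2.6 counted progressions.

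**The case against.** A reader might infer that the plan assigns diabetes status by history alone, and therefore that the reported proportions will be too high in both arms. The documents do not support either as a settled fact. The history labels come from an imputation list and a missing-covariate rule, neither of which defines this at-risk set. Protocol 4 describes the no-diabetes group in terms that a patient at or above the SAP's own 6.5 threshold would not fit. Protocol 3.2 lists HbA1c in the screening panel drawn to determine eligibility. Since no eligibility criterion uses it, sorting patients by diabetes status is a plausible purpose. On that reading most of the problem is already handled, and what remains is about 2 patients in the central case. Pointing the other way, Protocol 4 caps established type 2 diabetes, and SAP 2.7 counts duration from a diagnosis date. The text is ambiguous.

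The percentages are also fragile. They rest on a distribution the documents do not give, and they shrink once real new onset is allowed.

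Finally, the consequence is contained. This is one of eight exploratory objectives, with no multiplicity claim. HbA1c is itself a secondary endpoint, evaluated separately in patients without diabetes and adjusted for baseline (SAP 1.1, 2.3, 6.2.5), and baseline HbA1c is tabulated by arm (SAP 5, 5.4). Glucose lowering will therefore be visible directly.

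All of this stands and limits the severity. It does not remove the gap: on either reading, the rule as written can score an unchanged patient as progressing.

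**Conclusion.** The point holds as a definitional gap of minor severity. The rule has no pre-treatment HbA1c condition, the at-risk set has no HbA1c limit, and the analysis does not adjust for baseline HbA1c.

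Its size depends on two unknowns: how baseline status is assigned, and how many patients in the group start at 6.5 or more. Under the assumed distributions, with no true change, history-only classification puts about 1 to 16 of 174 patients at 6.5 or more at randomization, most of whom would be called progressors in the three cases shown. With screening HbA1c below 6.5 already required, about 0.2 to 4 patients in total are miscounted. Any inflation of the progression proportions is conditional on such patients being in the set. Type I error and the primary KCCQ analysis are untouched.

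**What to change.** In SAP 4.3 and 6.3.5:
- Limit the at-risk set for this endpoint to modified ITTS patients with no history of diabetes and HbA1c below 6.5 at both screening and randomization.
- Count progression as a first HbA1c of 6.5 or more at week 6 or week 12 in that set.
- List, per arm, the patients excluded because HbA1c was already 6.5 or more.
- Name the analysis set explicitly. SAP 2.1 gives the modified ITTS, while 6.3.5 borrows 6.3.2, which uses the safety set.

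Leave the stratification factor and the primary ANCOVA covariate unchanged.

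The cost is SAP wording only, since both pre-treatment HbA1c values are already scheduled. The exploratory denominator shrinks. Under the history-only model it falls from 174 to about 173, 162 or 151 in the three cases above, and there are fewer events. Some calls from measurement noise remain, about 4 of 12 in the central case, so the fix removes the already-elevated patients but not every spurious call.

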5.1 Demographics and Baseline Characteristics

- Age
- Sex
- Race/Ethnicity

5.2 Medical History

5.2.1 Diabetes History

- Diabetes duration
- History of diabetic peripheral neuropathy
- History of diabetic autonomic neuropathy
- History of diabetic retinopathy
- History of diabetic ketoacidosis (DKA) event
- History of hyperosmolar hyperglycemic syndrome (HHS) event
- History of severe hypoglycemic event(s)
- History of amputation

5.2.2 Other Medical History

- History of heart failure
- NYHA Class
- Most Recent LVEF Assessment
- History of PAD
- History of hypertension
- History of coronary artery disease
- History of dyslipidemia
- History of angina
- History of atrial fibrillation
- History of atrial flutter
- History of MI
- History of PCI
- History of CABG
- History of ventricular tachycardia
- ICD implanted

- Permanent pacemaker implanted
- History of valve disease

5.3 Physical examination

- Body Mass Index
- Sitting Pulse and Blood Pressure
- Supine Pulse and Blood Pressure
- Standing Pulse and Blood Pressure

5.4 Lab results

- HbA1c
- BNP
- NT pro-BNP
- Glucose (mg/dL)
- BUN - urea nitrogen (mg/dL)
- Creatinine (mg/dL)
- Estimated Glomerular Filtration Rate (eGFR)
- Sodium (mmol/L)
- Potassium (mmol/L)
- Chloride (mmol/L)
- Carbon Dioxide (mmol/L)
- Calcium (mg/dL)
- Phosphate - as phosphorus (mg/dL)
- Albumin (g/dL)
- Random Urine Creatinine (mg/dL)
- Random Urine Microalbumin < 0.2 mg/dL
- Random Urine Microalbumin (mg/dL)
- Enter Urine Albumin result, if measurable.
- Random Urine Albumin/Creatinine Ratio (mcg/mg creat)

6 EFFICACY ANALYSES

6.1 Analysis of the Primary Efficacy Endpoint

Analysis of the primary efficacy endpoints will be performed on the modified ITT data set, first on the entire cohort, then within the subgroups of patients with and without diabetes, and then within other subgroups as specified in section 2.3. Sensitivity analyses will be performed as outlined in section 2.3; in addition, supportive analyses will be repeated using the same models on the on-treatment set (OTS) and per-protocol set (PPS), as applicable.

Mean, standard deviation, median, and interquartile range (IQR) will be reported for KCCQ clinical summary score and for its change at 12-week follow-up, for the entire cohort and by treatment group.

An ACCOVA model will be used to estimate the effect of dapagliflozin on the 12-week KCCQ clinical summary score, adjusting for baseline KCCQ clinical summary score, sex, eGFR, Diabetes status, permanent atrial fibrillation status, and LVEF. Patient participation in the Echocardiography sub-study will not be controlled for because we don't hypothesize that participation in the Echocardiography sub-study is associated with the primary outcome (KCCQ CS).

A sensitivity analysis will repeat the primary analysis but will also include site as a random effect to account for potential clustering by enrolling center. Another sensitivity analysis will be performed using the imputed KCCQ values as described in section 2.6.

